Sample size and Justification: The traditional rule of thumb for sample size in logistic and Cox regression is ten events per predictor.⁷¹⁻⁷³ However, more recent simulation studies have revealed that serious problems aren't experienced until the number drops below five events per predictor.⁷⁴ Given the close association between logistic, Cox, and proportional odds regression models, these studies should provide a reasonable benchmark for sample size determination for our study. Thus, we adopted a rule of seven events per predictor in determining an appropriate sample size. Assuming that 1 contextual-level factor, 2 clinic-level factors, and seven patient-level factors (one socioeconomic, one cognitive, one psychological, one social, one related to accessibility to clinics, and one related to health status) will be significant at the 0.20 level in bivariate proportional odds models and that we'll need five additional terms due to polynomial trends or predictor-by-time interaction effects, our initial models for backward selection will require 105 events. We anticipate that 20% will be lost to follow-up in the first six weeks and 5% will be lost each year thereafter. Thus, for our loss to follow-up model we only require 378 participants.

However, we expect a cumulative MTCT rate of 5% by 24 months that suggests we will need 2,100 participants for this analysis assuming complete follow-up. Accounting for the expected drop-out, we will need to recruit $2100/(0.8*0.95*0.95) = 2,909$ participants. Assuming an average of 10 HIV diagnoses per year at eligible clinics, we will need to enroll in about 105 MCH clinics (3 per districts) in the first three years of the study.

C. Measurement / Instrumentation

Outcomes and measurement: Key programmatic outcomes that will be considered include: loss-to-follow-up (the proportion of HIV+ pregnant women initiated on ART for whom the whereabouts is unknown), retention in care (proportion of participants who are known to be receiving care), non-adherence to scheduled visits (proportion of participants whose whereabouts is unknown or who are in care but have missed at least one scheduled visit over the evaluation period), virological suppression (undetectable viral load), and MTCT rates (proportion of infants born to participating women who are tested positive for HIV).

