We will use a backward selection methodology to build a proportional odds model for each outcome consisting of contextual, clinic-level, and patient-level predictors. Within clinic-level clustering will be accounted for using Generalized Estimating Equations (GEE). Given the large volume of predictors being considered in this aim, we will only include predictors in our initial models for backward selection if significant at the 0.2 level in a bivariate (single predictor) model. At each step of backward selection, variables insignificant at the 0.1 significance level will be removed from the model.

Statistical analyses – Aim 2: The frequencies of outcomes will be compared between the intervention and control groups using adjusted Pearson's Chi-square.⁷⁷ All analyses will be intent-to-treat, meaning that women will be kept in their randomized group independent of whether they actually received (or did not receive) all their care in the group. The intervention and control groups will be compared for baseline prognostic factors and any imbalances that persist after randomization will be adjusted for using logistic regression. Within district- and clinic-level clustering will be accounted for using GEE.

Human subjects' involvement and characteristics

This study will involve HIV-infected pregnant women and their HIV-exposed infants who receive care in one of the maternal and child health clinics providing HIV care in Kinshasa. Clinical record of those participants (mother-infant register) will be accessed by the study team to extract data for the outcomes. In addition those mother will be interviewed on regular basis on sensitive subject

related to their HIV status, social support including relationship with partner. In addition to the discomfort associate with the discussion of such personal topic, there is a potential risk for confidentiality breach associated with the study.

To minimize those risk, all study staff will be retrained on ethical conduct of human subject research. As part of PEPFAR funded routine services for gender-based violence, resource are available at the level of those MCH clinic to provide psychological support for participant who might need them.

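### Aim 1 selects predictors by p-value with no allowance for the selection, so a substantial share of the factors it names would be expected to be false

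*Combined protocol and SAP*

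**What the plan says.** Section III.D (Statistical Analysis, Aim 1) names two primary outcomes for this aim, loss to follow-up and MTCT over 24 months, and builds a discrete-time proportional odds model for each. The predictor pool is described only by the words "Given the large volume of predictors being considered in this aim". The rule has two steps: "we will only include predictors in our initial models for backward selection if significant at the 0.2 level in a bivariate (single predictor) model"; then "At each step of backward selection, variables insignificant at the 0.1 significance level will be removed from the model". Clinic-level clustering is handled by GEE.

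Section III.B (Sample size and Justification) states that "we adopted a rule of seven events per predictor in determining an appropriate sample size". It begins "Assuming that 1 contextual-level factor, 2 clinic-level factors, and seven patient-level factors", assumes that these will pass the 0.20 screen, adds five further terms, and concludes that "our initial models for backward selection will require 105 events". It also names a danger point, reporting from simulation studies that serious problems do not appear "until the number drops below five events per predictor".

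Neither section says how many candidates will be tested. Neither describes multiplicity control, shrinkage, resampling or validation, or calls Aim 1 exploratory. The documents do not say whether confidence intervals will be reported for the Aim 1 models.

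**The concern.** Identifying health-system factors is one of the study's two objectives, and the rationale (Section II) says the findings will guide where and how the quality-improvement intervention is scaled up. A rule that tests many predictors against the outcome and keeps whatever stays below 0.1 will retain some that have no effect. Nothing in the plan would let a reader tell these from the real ones. Ordinary standard errors from the final model treat its terms as if they had been chosen in advance.

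The events budget adds a second issue for MTCT. Seven events per predictor is applied to the terms assumed to survive the screen, although the same outcome data are used to choose those terms from a larger pool.

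**Working it through.** **Reproducing the plan's figures (Section III.B)**

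- Terms: 1 + 2 + 7 + 5 = 15. Events: 7 × 15 = 105, as stated. (The text counts seven patient-level factors but lists six; with six, 7 × 14 = 98.)
- Retention: 0.8 × 0.95 × 0.95 = 0.722, so 0.278 are lost.
- Loss to follow-up model: 105 / 0.278 = 377.7, giving 378.
- MTCT model: 105 / 0.05 = 2,100; 2,100 / 0.722 = 2,908.6, giving 2,909.

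All the stated figures reproduce.

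**Events per candidate examined**

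The pool size is an assumption. A tally of the constructs named in Section III.C gives about 40 (about 20 patient-level and 20 facility-level); the range taken is 20 to 60.

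- MTCT: 105 / 20 = 5.25; 105 / 40 = 2.6; 105 / 60 = 1.75. Since 105 / 5 = 21, the ratio falls below five with more than 21 candidates.
- Loss to follow-up: 2,909 × 0.278 = 809 events. 809 / 15 = 54 per budgeted term; 809 / 40 = 20 and 809 / 60 = 13 per candidate. There is no shortfall.

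**False factors expected from the rule**

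A null predictor independent of the others is retained with probability of about 0.1, the deletion threshold. With 5 real factors, 20, 40 and 60 candidates contain 15, 35 and 55 nulls, so about 1.5, 3.5 and 5.5 false factors are expected.

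**Simulation of the stated rule**

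The simulation used logistic regression, a 0.2 screen, backward deletion at 0.1 and independent subjects. MTCT scenarios had 2,100 women, about 5% events and 150 runs each. The loss to follow-up scenario had 2,909 women, about 28% events and 100 runs. Odds ratios are per SD. Coverage is for nominal 95% intervals over all retained terms.

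| Outcome | Candidates | Real factors, OR | Correlation | False / all retained | False share | Coverage |
|---|---|---|---|---|---|---|
| MTCT | 20 | 5, 1.20 | 0 | 1.53 / 4.32 | 35% | 76% |
| MTCT | 40 | 5, 1.20 | 0 | 3.75 / 6.70 | 56% | 69% |
| MTCT | 60 | 5, 1.20 | 0 | 5.90 / 8.88 | 66% | 65% |
| MTCT | 40 | 5, 1.35 | 0 | 3.45 / 8.10 | 43% | 76% |
| MTCT | 40 | 10, 1.20 | 0 | 3.03 / 8.98 | 34% | 80% |
| MTCT | 40 | 5, 1.20 | 0.2 | 1.58 / 3.97 | 40% | 77% |
| Loss to follow-up | 40 | 5, 1.20 | 0 | 3.52 / 8.52 | 41% | 77% |

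- In these scenarios at least one false factor remained in 78% to 100% of runs.
- Coverage was about 45% to 50% for retained null factors and 93% to 97% for retained real ones.
- For MTCT, a true OR of 1.20 averaged about 1.29 when selected: ln 1.29 / ln 1.20 = 0.255 / 0.182 = 1.40, or 40% too large on the log-odds scale. A true OR of 1.35 averaged 1.37. For loss to follow-up, 1.20 averaged 1.20.

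A separate MTCT simulation used 105 clinics, half the candidates at clinic level and clinic-robust standard errors. With 40 candidates and 6 real factors at OR 1.22, 3.7 of 7.1 retained factors were false (52%).

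**The case against.** Four counter-arguments carry weight.

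- **The pool size is not in the documents.** This stands. The number of false factors scales with the count of nulls and falls with correlation: at 40 candidates, a correlation of 0.2 cuts it from 3.75 to 1.58. Even so, 40% of retained factors were false in that case.
- **The event count does not cause the false factors.** This also stands. A reader might infer that seven events per assumed survivor is what fills the model with noise. The loss to follow-up model has about 809 events and still keeps 3.52 false factors of 8.52. The cause is uncorrected retention at 0.1, which more events alone would not remove.
- **The plan specifies no Aim 1 intervals.** A reader might infer that its error bars are wrong as written, but there is no text to support that. The low coverage is concentrated in null terms and is close to arithmetic: a null kept because p < 0.1 has a 95% interval that excludes no effect whenever p < 0.05, which is about half the time.
- **The 15-term budget need not be overrun.** With independent predictors, an average of 6.6, 11.0 and 15.0 of 20, 40 and 60 candidates passed the screen; with correlation 0.2, 29.2 of 40 did. Because the documents give neither the count nor the correlation, an overrun is possible but not established. Nor do they say that the events rule must count every candidate.

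Both simulations also used ordinary logistic regression, not the planned discrete-time model with time-varying covariates, so the percentages are indicative.

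**Conclusion.** The point holds as a reporting and validation gap that is inexpensive to close. As written, Aim 1 will name factors by a rule that retains roughly one in ten independent nulls, with nothing to separate them from real factors. On an assumed pool of 20 to 60 candidates, about a third to two thirds of the factors retained for MTCT would be false; for loss to follow-up, about 40% at 40 candidates. Naive intervals, if given, would under-cover, mainly for null factors.

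Two parts apply to MTCT only: events per candidate below five once more than 21 are examined, and overstatement of modest real effects that are selected. It would be wrong to extend either to loss to follow-up. It would also be wrong to conclude that the sample size must rise. Seven events per candidate at 40 candidates would mean 280 events and 280 / 0.05 / 0.722 = 7,757 women, and false factors would still be retained at the 0.1 level. The randomised comparison in Aim 2 is unaffected.

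**What to change.** In Section III.D (Aim 1):

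1. Fix and list the candidate predictors before any outcome data are analysed.
2. For each outcome, repeat the whole procedure (0.2 screen and backward deletion) in at least 500 bootstrap resamples of districts.
3. Report inclusion frequencies and bootstrap intervals beside the final model.
4. Call a factor identified only above an inclusion frequency set in advance, and describe the other retained factors as exploratory.

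In Section III.B, state that seven events per predictor refers to terms assumed to pass the screen, and give the MTCT events per candidate for the listed pool.

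The cost is analysis-plan wording and computing time, with no new data or visits. The downside is that fewer factors will be declared, including some weak real ones, and intervals will be wider.

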
I. Objectives

The study has two specific objectives:

- 1- **To identify modifiable health delivery system factors associated with retention in care and sustained virological suppression in HIV-infected women in MCH clinics.** We will use surveys of health facilities, including selected staff, and service beneficiaries (HIV infected mothers) to collect data on key characteristics of the service delivery's organization and providers' and patients' perspective of the HIV care delivery performance. Proportional odds models will be used to identify key modifiable characteristics associated with the main outcomes (LTFU, virological suppression, and MTCT rate).
- 2- **Evaluate the effectiveness of CQI interventions in improving long-term retention in care and virological suppression in HIV-infected women in MCH clinics.** We will conduct a cluster-randomized trial with health districts as the randomization unit. MCH clinics in the

intervention group, will undergo quality improvement initiatives using participatory data-driven approaches and on-site monitoring and supervisory support.

II. Background and Rationale

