Quality Improvement Collaborative is one of the most popular methods for organizing sustained improvement efforts at hospitals and ambulatory practices worldwide.⁶⁻⁸ In the Breakthrough Series approach (henceforth refer to as continuous quality improvement (CQI)),⁹ quality improvement (QI) teams from multiple sites across a region or country are brought together to focus on a common problem. Over one or two years, experts in clinical and performance improvement provide the group with periodic instructions and encourage the teams to share lessons learned and best practices. Starting in 2010, South Africa used QI interventions to inform improvement in the health delivery system to successfully scale-up a highly performing national PMTCT program over a short period of time. The use of CQI is thought to have played a key role in the program's success.¹⁰⁻¹⁴ However, despite its popularity, the effectiveness of CQI as a strategy to improve retention in care and long-term outcomes of HIV care in MCH clinics has never been demonstrated in a randomized trial or a well-designed comparative study and it remains to be shown whether the South African experience can be replicated in settings with fewer resources.¹⁵

If the CQI interventions are proven to be effective in improving long-term outcomes of therapy in MCH clinics, it will provide PEPFAR and other critical stakeholders with a scalable strategy to strengthen the quality of HIV continuum of care that can be implemented in combination with sustained efforts to expand coverage. Identification of health system delivery characteristics associated with improved long-term outcomes will help determine where and how the CQI interventions can be effectively scaled up to support PEPFAR goal of an AIDS-free generation.

III. Procedures

A. Research Design

This cluster randomized controlled study will be implemented in two phases. In Phase I, we will collect information on the key characteristics of the healthcare delivery system in the facilities participating in the study. We will also strengthen the current monitoring and evaluation system in MCH clinics to establish a robust system capable of collecting individual patient-level data necessary for the timely production of indicators and monitoring of program outcomes. Phase II

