will start with the randomization. At the beginning of this phase, using the baseline data collected in Phase I, we will bring together teams from the health district Bureau (responsible for supervision), and from sites in the intervention group to identify key bottlenecks in the care delivery system. The group will also develop and agree on an action plan to modify the priority bottlenecks and the key indicators to include in the quarterly data for actions reports. As part of the final evaluation of the 5-year CQI intervention in participating clinics and health zones of Kinshasa, we will conduct semi-structured in-depth questionnaires with members of CQI teams in MCH clinics and at the health zone level. These qualitative data will allow to evaluate the intervention's implementation process measures. Specifically, qualitative interviews will allow to: 1) Investigate contextual factors important for the way intervention was understood, implemented, and adopted by participating personnel and administrators of MCH clinics and health zones; 2) Examine factors that impact the application, quality, and sustainability of the intervention; 3) Understand the attitudes towards the CQI intervention at different levels (individual, facility, and health zones) and possibilities of its future use and scale-up in DRC to reduce mother-to-child HIV transmission.

This two-phased approach will provide us time to thoroughly assess the health delivery characteristics for Aim 1. The study will be implemented in Kinshasa, Democratic Republic of Congo (DRC) and in collaboration with the University of Kinshasa's School of Public Health (KSPH).

B. Sample

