Sampling strategy: According to the National AIDS Program, there are a total of 295 MCH clinics in Kinshasa currently providing PMTCT services. To inform selection, study staff will obtain information on factors that might affect the quality of care provided in each facility including: the type of management, location (health district), number of deliveries, number and type of personnel, and onsite HIV pediatric care. This information will be used to stratify clinics. Within each stratum, a random sample of facilities will be taken within each of the 35 health districts in Kinshasa. This selection scheme is adopted to ensure, for example, that health care facilities at the center of the city, which might have lower patient volumes and more patients with higher socio-economic status than facilities in peri-urban areas, are included in the final sample to ensure that the sampled clinics are representative of all clinics of similar size across the province. Clinics will be excluded if less than 500 pregnant women (less than 5 HIV-infected pregnant women) registered for antenatal care (ANC) in the clinic in 2015. All women diagnosed with HIV during pregnancy or breastfeeding in the participating MCH clinics and initiated on ART during the enrollment period and their HIV-exposed infants will be eligible for the study.

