In 2010, as part of our technical support to the implementation of PMTCT in Kinshasa, we developed and supported the implementation of a mother-infant register in 105 MCH clinics to monitor PMTCT care provided in these clinics. The registry was modeled after the WHO's Three Interlinked Patient Monitoring Systems for HIV Care/ART, MCH/PMTCT (including malaria prevention during pregnancy), and TB/HIV: Standardized Minimum Data Set and Illustrative Tools. The register is used to track important HIV care events among HIV-infected pregnant women and subsequently their HIV-exposed infants, from the first contact with the ANC clinic through delivery and the effective linkage of the mother-infant pairs to HIV care and treatment (C&T) services. The following key information is documented in the register: a maternity code that is used to link mother and infant, address and telephone number, gestational age at HIV diagnosis, date of birth, date of reference to HIV C&T if any, date of first visit at C&T and a code number assigned to the mother at C&T, and other information necessary to calculate PEPFAR's PMTCT indicators. For mother-infant pairs who still need to integrate HIV C&T services after delivery, information on infant feeding practices, cotrimoxazole prophylaxis at subsequent visits, date of first sample collection for early infant diagnosis at six weeks and the result, a second sample collection and result at nine months, and eventually a serological test at 18 months for all infants with HIV-negative PCR results is also documented. For real time use of information in the register, nurses who supervised the implementation of PMTCT technical assistance were each equipped with a laptop including the electronic version of the register (in the open-source software Epi-info) and at each clinic visit, they extracted information for the register into the electronic database and returned the updated database to the central team. The same scheme was used for monitoring in our study on conditional cash transfers with a group of nurses who successfully visited on a regular basis the 90 MCH clinics that were enrolled to extract the data in the electronic database. Because of its success, the register has been adapted by the PNLS for the monitoring of Option B+. We will rely on the register to obtain information on the outcomes with study nurses visiting the clinics on regular basis to extract key information for the study into the database.

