gaps in the service delivery. The team will develop a priority action plan to address the main gaps and agree on a set of key indicators representing critical points in the PMTCT cascade that will be used to monitor the changes resulting from the implementation of the action plan. Thereafter, the health district QI team and a study team member will visit each clinic at least once a month to supervise and support the implementation of the action plan. Every quarter, using data from the monitoring system (Aim 1), the study team working with the provincial coordination of the National AIDS Program (cPNLS) will generate a quarterly report including a color-coded dashboard for tracking changes using the 'traffic light' approach. An indicator will score green when the target has been achieved, yellow/amber when there is a progress from the baseline value without reaching the target, and red when there is no progress or downward movement. Figure 6 outlines the cascade that was followed in South Africa and highlights the indicators used at critical points in the cascade to support tracking progress and identification of gaps in service delivery.¹⁴ A similar cascade will be created with indicators agree upon with the QI teams. The report will be generated for each participating clinics in the intervention group and shared with the cPNLS, the QI teams, and the management of the clinic. QI teams will be brought together to review these indicators, share experience, identify remaining gaps in the service delivery, and develop a new priority action plan for the next quarter.

Statistical Analysis –Aim 1: The primary outcomes for this aim are loss to follow-up and MTCT over the first 24 months of follow-up. Since the characteristics of interest in this aim may vary with time and a substantial proportion of participants may drop out prior to study conclusion or MTCT, both outcomes will be modeled using a proportional odds model for discrete time survival data.⁶⁹ At each follow-up time, the proportional odds model assumes that the log-odds that an event (loss to follow-up or MTCT) has occurred by that time point is a linear function of a time-dependent intercept plus covariates, some of which are time-varying. The model also assumes that the odds ratio comparing two different levels of a covariate is constant over time (i.e., proportional odds).

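### Aim 2 does not prespecify the pre-randomisation district (or clinic) rate of the primary outcomes as a covariate, which may cost precision in the CQI effect but causes no bias

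*Combined protocol and SAP*

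**What the plan says.** **Design.** The Objectives state: "We will conduct a cluster-randomized trial with health districts as the randomization unit". Section III.B adds that "a random sample of facilities will be taken within each of the 35 health districts in Kinshasa", and plans for about 105 clinics, three per district.

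**Aim 2 analysis (III.D).** The main comparison is: "The frequencies of outcomes will be compared between the intervention and control groups using adjusted Pearson's Chi-square". The same paragraph compares the arms on baseline prognostic factors, adjusts by logistic regression for imbalances that remain, and handles district and clinic clustering with GEE. It names no covariate.

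**Baseline information.** Under III.A, Phase I comes before randomisation. It describes the participating facilities and strengthens a monitoring system capable of "collecting individual patient-level data necessary for the timely production of indicators and monitoring of program outcomes". Phase II opens by identifying bottlenecks "using the baseline data collected in Phase I". In III.D the dashboard scores an indicator "yellow/amber when there is a progress from the baseline value without reaching the target". Section III.C says of the mother-infant register: "Because of its success, the register has been adapted by the PNLS for the monitoring of Option B" (that is, Option B+). It also makes the register the source of the trial outcomes and lists the six-week infant test result among its entries.

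**The concern.** A woman has no baseline value of LTFU or infant testing, but her district and clinic have a history. A cluster's earlier rate of an outcome is often a good predictor of its later rate. With about 35 randomised districts, differences between districts can dominate the standard error of the CQI effect. GEE and the clustering-adjusted chi-square carry that variance into the standard error but do not reduce it. A baseline rate in the model can remove part of it, and does so even when the arms are balanced on it.

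The imbalance rule does not secure this gain. It depends on what the data show after allocation, so a strong predictor that happens to be balanced would stay out. What is at stake is power for the two primary outcomes. Section III.B sizes the study only by events per predictor and states no power for Aim 2, so there is no documented margin to give away. The dashboard would also judge clinics against their own baseline while the trial's effect estimate need not.

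**Working it through.** **1. The plan's own figures (III.B).** Retention at 24 months = 0.8 × 0.95 × 0.95 = 0.722, so LTFU = 27.8%. Then 105/0.278 = 377.7, giving 378, and 2,100/0.722 = 2,908.6, giving 2,909. Both reproduce. They come from the events-per-predictor rule, so they say nothing on power for Aim 2.

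**2. Inputs.** From the plan: 35 districts; 2,909/35 = 83.1 women per district; control LTFU 27.8%; 3 clinics × 10 diagnoses a year = 30 women per district per year. Assumed, because the plan is silent: ICC 0.01 to 0.10, an 8-point reduction, a 17:18 split, a two-sided 5% t-test on district rates, one year of baseline data (30 women per district), and a correlation of 0.6 or 0.8 between true district rates over time.

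**3. Correlation a noisy baseline can reach.** Reliability of a rate from n women = n × ICC / (1 + (n − 1) × ICC). The observed correlation ρ is the over-time correlation × √(baseline reliability × follow-up reliability). At ICC 0.05: baseline 1.5/2.45 = 0.61; follow-up 4.16/5.11 = 0.81; ceiling √(0.61 × 0.81) ≈ 0.71; ρ ≈ 0.42 (over-time 0.6) or 0.56 (0.8).

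**4. Power.** Design effect = 1 + 82.1 × ICC. Variance of a district rate = 0.278 × 0.722 / 83.1 × design effect. SE of the difference = √(variance × (1/17 + 1/18)), multiplied by √(1 − ρ²) when adjusted. Power is from the noncentral t with 33 df (32 adjusted). For simplicity the control-arm variance is used in both arms. At ICC 0.05 the SE is √(0.01234 × 0.1144) = 0.0376, and power is 54%. With over-time correlation 0.8 the SE is 0.0376 × √(1 − 0.319) = 0.0310, and power is 71%.

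| ICC | Design effect | Ceiling on ρ | ρ at 0.6 / 0.8 | Variance cut | Power, unadjusted | Power, adjusted (0.6 / 0.8) |
|---|---|---|---|---|---|---|
| 0.01 | 1.82 | 0.33 | 0.20 / 0.26 | 4% / 7% | 93% | 94% / 95% |
| 0.02 | 2.64 | 0.49 | 0.29 / 0.39 | 9% / 15% | 82% | 85% / 88% |
| 0.05 | 5.11 | 0.71 | 0.42 / 0.56 | 18% / 32% | 54% | 63% / 71% |
| 0.10 | 9.21 | 0.83 | 0.50 / 0.67 | 25% / 44% | 34% | 43% / 54% |

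**5. Simulation check.** District-level regression, 6,000 runs per case, 30 baseline and 83 follow-up women per district:

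- Over-time correlation 0.6: 83.7% to 85.7% (ICC 0.02), 54.6% to 62.5% (0.05), 32.9% to 41.6% (0.10).
- Over-time correlation 0.8: 83.1% to 88.4%, 55.0% to 70.7%, 34.0% to 51.9%.
- Type I error at ICC 0.05: 5.4% unadjusted, 5.0% adjusted.

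Formula and simulation gains agree to within about three points. Simulations with other variance models give gains of the same order, which is why the ranges in the verdict are rounded.

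**6. As a detectable difference.** If r is the correlation of the baseline rate with the underlying follow-up district rate, the design effect becomes (1 − ICC) + 83.1 × ICC × (1 − r²). At ICC 0.05 and r = 0.5 this is 0.95 + 4.156 × 0.75 = 4.07, against 5.11. The LTFU difference detectable with 80% power falls from 10.1 to 9.1 points.

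**The case against.** The strongest reply is that the baseline rate is inferred. Phase I is said to describe facilities and build a system able to collect patient data; the contents of its baseline data are not listed. The dashboard indicators are agreed after randomisation, and reports go to intervention clinics only. Nothing says that a baseline rate of either primary outcome exists, covers control clinics, or is summarised by district. The register began in 105 clinics, but these are not said to be the study clinics. This stands in part: availability is implied, not stated. But Phase I covers all participating facilities, and the register is the trial's outcome source, so the expectation is reasonable.

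Three stronger readings are tempting, and the documents do not support them:

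- A reader might infer that the plan shuts the baseline rate out. It does not: the rate could enter as an imbalanced prognostic factor. It is simply not prespecified.
- A reader might infer bias or an invalid test. Neither follows from omitting a prognostic covariate here.
- A reader might take ρ = 0.5 at every ICC, which at ICC 0.02 gives a gain of about 8 to 9 points. With 30 baseline women the ceiling there is 0.49 even if true rates never change, so that gain is not realistic.

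Two further limits stand. The calculations cover LTFU only; nothing is computed for infant diagnosis, or for early loss as a proxy for 24-month loss, which would lower the correlation. They also describe a district-level test. In a simulation of a GEE logistic model with the usual sandwich variance and 35 districts, type I error was 7.3% to 7.6% with z tests and about 6.3% with t on 32 df, so the near-5% result does not carry over to uncorrected GEE.

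**Conclusion.** The point holds as a worthwhile improvement, not as an error that invalidates Aim 2. A baseline rate of the primary outcomes can now enter only through a data-driven rule, and the price is precision. Under the stated assumptions the power gain for LTFU is about 2 to 5 points at ICC 0.02, 7 to 16 at 0.05 and 9 to 20 at 0.10. It is little or nothing at ICC 0.01, or if baseline rates predict poorly. The gain is largest where unadjusted power is weakest. All of this rests on an ICC, an effect size, a baseline period and an over-time correlation that the plan does not give. For timely infant diagnosis the direction is the same, but no size can be claimed.

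**What to change.** In III.D, Aim 2:

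- **Covariate.** In the GEE logistic model for LTFU and for timely infant diagnosis, prespecify the district's (or clinic's) pre-randomisation rate of the same outcome, whatever the observed imbalance. State that this model supplies the CQI effect estimate, with the adjusted chi-square as support.
- **Source.** Use Phase I data or register entries dated before randomisation, from clinics in both arms, and fix the values before outcomes are compared by arm. This remains possible after allocation.
- **No 24-month baseline.** Use early versions: loss by six weeks and the first infant PCR result. The plan expects 20 of its 27.8 points of loss in the first six weeks, and the register records the six-week test.
- **Inference.** Use a small-sample-corrected variance with a t reference, or a district-level regression, given about 35 clusters.

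**Cost.** A few sentences, one between-district degree of freedom (33 to 32), and one register extract that includes control clinics. Eligibility in III.B is limited to women starting ART in the enrolment period, and the consent section requires written consent from all subjects. The team should therefore confirm that ethics approval covers aggregate register data from before enrolment. No extra participants or visits are needed.
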